6.0 Data and Specimen Banking

6.1 Storage and Access:

Biomarker specimens will be collected and stored at the study site in Hawai'i until shipment to the Masonic Cancer Center's Drs. [name] and [name] laboratories for analysis or long term storage. Shipments may be requested at approximately quarterly intervals. Samples that are not used for the primary analysis of study biomarkers will be banked for future use. The banked samples will be stored until requested by a qualified investigator and used up or destroyed if it is determined they are no longer needed. The samples, including DNA or RNA, may be stored up to a maximum of 20 years from the study's end. A participant has the right to withdraw consent at any time by informing the Principal Investigator by following the instructions provided in the consent documents. If this occurs, any remaining identifiable research sample(s) will be destroyed.

6.2 Data:

Biomarker samples (blood components and urine) that are banked after the completion of the primary analyses will be stored at the Masonic Cancer Center [name] and [name] laboratories located at the Cancer and Cardiovascular Research Building for future use.

Local data will be stored at the study site at the University of Hawai'i Cancer Center. This data will be provided to the other Program Project Investigators as needed to conduct their study. Shared data will be de-identified and includes demographics, tobacco/nicotine exposure history and current use, health and medications, participative questionnaire data, and biomarkers analyses.

6.3 Release/Sharing:

We intend to share findings from this research through publications and presentations. Institutions and individuals wishing to access any resources or data must contact the Principal Investigator. Data will be available in two formats. One will be a summary of the data, with graphs and tables, posted as pdf files and as raw individual-level data for analysis. Data generated by this grant will be made to outside investigators, according to NIH Guidance. When data are shared, there will be no limits placed on how the data will be used, and co-authorship is not required as a condition for receiving data. Users will agree, however, that the recipient must not transfer the data to other users and that the data are only to be used for research purposes. A record of transfer of data and a copy of the dataset that was distributed will be kept by University of Minnesota.

7.0 Sharing of Results with Participants

7.1 Results of the study

No individual data will be shared with the participants.

8.0 Study Population

8.1 Inclusion Criteria:

- a) Japanese American – one, but preferably 2 biological parents of Japanese descent;
- b) Male or female 21 years or older (adolescents/young adults under the age of 21 will be excluded);
- c) Daily smoker > 5 cigarettes for at least 3 months;
- d) Eligible urinary ratios of total 3-HCOT to cotinine:
 - o "Little or no-CYP2A6 activity" defined as a ratio of <0.6 or;
 - o "Relatively high" CYP2A6 activity defined as a ratio of >3.0.
- e) Stable and good physical health;
- f) Stable and good mental health (e.g., not experiencing unstable or untreated psychiatric diagnosis, including substance abuse, within the past 3 months);
- g) Provided written informed consent to participate in the study.

8.2 Exclusion Criteria:

- a) Unwilling to avoid other nicotine containing products during the study and no use of any nicotine-containing products except cigarettes for 1 week prior to their study visits);
- b) Currently taking any medications that affect relevant metabolic enzymes or anti-inflammatory medications such as ibuprofen (this will be reviewed by study investigators on a case-by-case basis);
- c) Active infection (e.g., influenza, cold, respiratory infection, sinus infection) at the time of enrollment);
- d) Experiencing medical conditions that might affect biomarkers of exposure and effect;
- e) Pregnant or nursing or planning on becoming pregnant during the study;
- f) Unable to read and understand English;
- g) Unable to identify ancestry.

8.3 Screening:

Participants are initially screened in Study 1: Observational Study where urine and blood samples were collected and analyzed to determine rate of nicotine metabolism. During Study 1, Japanese American participants were informed of the opportunity to participate in Study 2 if they meet the eligibility criteria. When eligible participants are identified, they will be provided with detailed description of the study and attend a Study 2 Screening visit where the study will be described in detail, and informed consent will be obtained prior to any study procedures. Participants have completed several forms as part of Study 1 and this information will be shared with Study 2. As part of the Study 2 Screening visit participants will complete:

- a) Brief Medical History

- b) Concomitant medications
- c) Tobacco Use Exposure and History Update
- d) NIAAA Alcohol Use Questionnaire-short form
- e) Fagerstrom Nicotine Dependence Questionnaire

Medical history will be reviewed by the study medical professional to determine eligibility.

9.0 Local Number of Participants

9.1 Local Number of Participants to be Consented:

Up to 50 participants will be consented in order to complete 20 participants. All participants will be recruited at the University of Hawai'i Cancer Center. No recruitment will occur at the University of Minnesota.

10.0 Recruitment Methods

10.1 Recruitment Process:

Participants are recruited from Study 1: Observation Study part of "Mechanisms of Ethnic/Racial Differences in Lung Cancer Due to Cigarette Smoking"

IRB ID: Study 00000335; University of Hawai'i IRB ID: 17649.

10.2 Identification of Potential Participants:

University of Hawai'i research staff will inform potential participants by phone that they are eligible to enroll in Study 2. These participants have already agreed to be contacted regarding the opportunity to participate in Study 2. Upon contact they can agree or decline further information and screening.

10.3 Recruitment Materials:

No additional recruitment materials will be used in this study beyond the Study 1 recruitment.

10.4 Payment:

Participants will receive \$40 for time and \$10 for travel for each of the 6 clinic visits (\$300); \$50 for each of the four 24 hour urine collections (\$200); \$10 for each of the 8 days of cigarette butt collections (\$80) and a bonus of \$250 for completing all study procedures. Payment is through the University of Hawai'i Cancer Center compensation method (gift card) to compensate for effort, time, and transportation for a total of \$750.

11.0 Withdrawal of Participants

11.1 Withdrawal Circumstances:

If a participant experiences an adverse event or no longer meet eligibility criteria (e.g., quit smoking) they will be withdrawn.

11.2 Withdrawal Procedures: If a participant is no longer eligible, they will be informed at the visit and data collection will stop. If withdrawal is due to an adverse event, appropriate follow-up will be completed.

11.3 Termination Procedures: No additional procedures will be completed however, data already collected may be used.

12.0 Risks to Participants

12.1 Foreseeable Risks:

Potential risks: The potential risks for participants are minimal.

In this Clinical Study, the risks in this study include:

- 1) Loss of privacy due to a breach in confidentiality;
- 2) Risk of pain, bruising or infection at the site of the phlebotomy; and
- 3) Use of study cigarettes.

Protection against breach of confidentiality:

Participants will be told their participation in the project will be strictly confidential, that any identifying information will only be available to the site investigators, coordinating center study manager, an auditor for the Food and Drug Administration, study sponsor or University of Hawaii's institutional oversight. No identifying information concerning the data and results will be made known. Participants will have written assurance that while de-identified individual participant data may be available to other researchers for research purposes, only a summary of the results will ever be published or otherwise publicly released. They will also be informed that all raw data will be coded with numbers and any identifiers will be kept in locked file cabinets and only appropriate study personnel will have access.

All data will be de-identified and transferred through a secure, password-protected website that is only available to the investigators. All identifying information will be in a locked in a secure place and accessible only to relevant study staff.

Risk with phlebotomy:

Blood samples will be obtained by a trained phlebotomist with single-use, sterile blood collection supplies to minimize the risk associated with a blood draw.

Smoking Study Cigarettes:

Clinical Study participants will be smoking cigarettes containing deuterium labeled NNK, which has not led to any adverse events in the studies that we have completed (NCT01158456, NCT00691132). To minimize risk, participants will have a review of their medical history prior to entry into this study to screen for any potentially compromising medical condition. Participants will be under medical supervision throughout their

participation in the clinical study and adverse symptoms will be recorded at each clinic visit and monitored by the study's health professional.

The study cigarettes pose the same risks of conventional cigarettes. Because smoking causes a multitude of diseases, if at any time the smoker wants to quit use of all tobacco products, this decision will be encouraged and supported. At the end of study, participants will be strongly encouraged to stop use of all tobacco products and to set a quit date, and will be provided with a treatment resources and referral to local treatment options.

Participants will be informed the study cigarettes contain the same risks as smoking any combustible tobacco product. Precautions would be similar to other tobacco products including smoking related health risks, secondhand smoke exposure and fire danger. Participants will be advised to keep out of reach of children or pets.

Throughout their participation in the study, adverse symptoms will be recorded at each clinic visit and monitored by the PIs and study medical personnel. Participants who experience any significant adverse side effects will be examined by a physician, sent or accompanied to the emergency clinic or referred to their physician, depending on the nature and severity of the side effect or adverse event.

12.2 Reproduction Risks: No additional risk to the fetus than the risk associated with conventional cigarettes. We will conduct a pregnancy screen of child-bearing women prior to providing study cigarettes to verify status.

12.3 Risks to Others: No additional risk of study cigarettes; all cigarettes pose a risk of exposure to second-hand smoke.

13.0 Potential Benefits to Participants

13.1 Potential Benefits: None

14.0 Statistical Considerations

14.1 Data Analysis Plan:

In subjects with little CYP2A6 activity we expect the metabolism through NNAL to be significantly higher and metabolism by α -hydroxylation to be much lower than in smokers with "normal" CYP2A6 activity. The extent of NNK α -hydroxylation in the two groups will be described by a ratio of NNK metabolites, D₄- α -hydroxymethyl NNK Gluc (or other products of α -hydroxylation) to D₄-NNAL. The ratio is used as a measure of the pathway as a percent of dose. The values are predicted to be lower in the smokers with little or no CYP2A6-activity.

Statistical considerations: Our comparison will be between the means (or if the distribution is highly skewed the medians or geometric means) of the two groups (null versus average CYP2A6). The power of the test depends

on the size of the group difference compared to the within-group variability, i.e. to the standard deviation of NNK α -hydroxylation. Assuming that a normal distribution holds we will have 80 percent power to detect a difference in group means amounting to about 0.9 standard deviations of the distribution of NNK α -hydroxylation. In these analyses we will adjust for potential confounders including age, sex, race, total nicotine equivalents, BMI, etc.

We will also compare the NNK metabolic profiles of the two groups. The beauty of this new profiling method is that several pathway will be analyzed at once allowing the characterization of the overall flux of NNK through its major metabolic pathways. The aim is primarily descriptive (characterizing the NNK metabolic profile) and hypothesis generating. Data analysis will use multivariate methods such as cluster analysis, pathway mapping, heatmaps and other statistical applications to characterize metabolites variation and covariation of NNK, NNAL-N-oxide, NNAL-glucuronides, α -hydroxy glucuronides and other NNK metabolites identified in smokers receiving [Pyridine D₄]-NNK

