Protocol Title	STUDY 2: CLINICAL PROTOCOL Metabolism of NNK Among Japanese Americans
Principal Investigator/Faculty Advisor	Name: [name].
	Department: Masonic Cancer Center
	[contact]
	Email Address: [contact]
Scientific Assessment	Nationally-based, federal funding organizations
IND/IDE # (if applicable)	IU0000492
IND/IDE Holder	[name]
UMN Investigational Drug Services #	5555RO
Version Number/Date:	Version 1 October 11, 2019

REVISION HISTORY

Table of Contents

Study Synopsis.....	4
1.0 Objectives.....	6
2.0 Background	6
3.0 Study Endpoints/Events/Outcomes.....	10
4.0 Study Intervention(s)/Investigational Agent(s)	10
5.0 Procedures Involved	11
6.0 Data and Specimen Banking	16
7.0 Sharing of Results with Participants	16
8.0 Study Population.....	17
9.0 Local Number of Participants.....	18
10.0 Recruitment Methods.....	18
11.0 Withdrawal of Participants	18
12.0 Risks to Participants	19
13.0 Potential Benefits to Participants	20
14.0 Statistical Considerations.....	20
15.0 Provisions to Monitor the Data to Ensure the Safety of Participants	21
16.0 Provisions to Protect the Privacy Interests of Participants	22
17.0 Consent Process.....	23
18.0 Setting	23
19.0 Multi-Site Research.....	23
20.0 References	24

Study Synopsis

Study Design:	
The risk of lung cancer varies by individual and by ethnic/racial group. In this study we will explore how individual differences in the metabolism of a tobacco-specific lung carcinogen may contribute to the variable risk of lung cancer between ethnic/racial groups.
 
In this 10 day clinical trial, Japanese Americans will smoke a cigarette containing deuterium-labeled 4-(methylNitrosamino)-1-(3-pyridyl)-1-butanone (NNK), a tobacco-specific lung carcinogen. The study cigarette will be smoked for 7 days.
 
This will allow for NNK metabolic profiling and determining the effect of CYP2A6 genotype on the level of NNK α -hydroxylation in Japanese Americans smokers using [pyridine- D4]-NNK containing cigarettes.

Primary Aim:	
• To characterize the bioactivation of NNK by α -hydroxylation;• To develop an NNK metabolite profiling method;• To determine the contribution of the enzyme CYP2A6 to NNK bioactivation.
Patient Population:	Japanese American Smokers
Accrual Goal:	20 completed participants
Enrollment Period:	January 1, 2019 through August 30, 2021
ITP #	IU0000492

ABBREVIATIONS/DEFINITIONS

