4.0 Study Intervention(s)/Investigational Agent(s)

4.1 Description:

The goal of this trial is to determine the effect of CYP2A6 genotype/phenotype on NNK α -hydroxylation in Japanese American (JA) smokers administered [pyridine-D₄]NNK for 7 days. Japanese American smokers (N=20 completers) will be recruited from the 100+ Japanese Americans participating in Study 1: Observation Study part of "Mechanisms of

Ethnic/Racial Differences in Lung Cancer Due to Cigarette Smoking" Clinical and Biomarkers Core.

4.2 Drug/Device Handling:

The study will use a commercial tobacco product that has [pyridine-D₄]NNK added to the tobacco thereby making it an investigational tobacco product. Natural American Spirit-Tan cigarettes (king size, hard pack) are commercially manufactured by the Santa Fe Natural Tobacco Company currently marketed by RJ Reynolds and are available for purchase in retail stores and online. The American Spirits-Tan were chosen because they have approximately 11% of the level of NNK found in other manufactured cigarettes. Natural American Spirit-Tan cigarettes will be modified by injecting [pyridine-D₄]NNK into the tobacco rod of these cigarettes so that the sum of the naturally present NNK and the added [pyridine-D₄]NNK is similar to or below the NNK levels found in typical commercial U.S. cigarettes.

Preparation of study cigarettes

The addition of [pyridine-D₄]NNK to study cigarettes will be carried out by following our previously established methods ¹⁶ American Spirit-Tan cigarettes will be purchased by University of Minnesota (king size, hard pack) which contain 0.21 - 0.37 µg NNK/g wet weight tobacco. The cigarettes will be modified by adding 0.300 µg [pyridine-D₄]NNK to each cigarette so that the amount of total (deuterated plus unlabeled) NNK in these cigarettes is below 0.700 µg/g tobacco which is the average NNK level in popular commercial cigarette brands. [Pyridine- D₄]NNK has been synthesized in our laboratory. The addition of [pyridine-D₄]NNK to the cigarettes will be carried out with a specially designed microsyringe applicator system. The prepared cigarettes will be conditioned at 25°C and 60% relative humidity for 2 days, placed back in their original packs, 20 cigarettes per pack, and stored at 4°C until being dispensed to study participants.

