5.0 Procedures Involved

[figure not shown]
5.1 Study Design:

In this clinical trial, the selection and recruitment will be determined based on the urinary ratios of CYP2A6-generated nicotine metabolites total 3-HCOT to cotinine. Little or no-activity is defined as a ratio of <0.6 (expected 12% for JA from previous MEC sample and "relatively high" is defined as a ratio of >3.0. (28% had a ratio >3 and 15% <0.6 expected for JA smokers in the previous MEC sample and had a median ratio of 1.8).

Japanese American smokers will be recruited for a study where they will smoke cigarettes that contain [pyridine-D₄] NNK. One group will be smokers with very low or no CYP2A6 activity and the other will have relatively high activity. Participants are selected from Study 1: Observational Study which provided human biological samples and measurements from Native Hawaiian, Japanese Americans and Whites.

In this study, participants will smoke the [D₄-pyridine]-NNK study cigarettes for 7 days and 24 hour urine samples and blood samples will be collected to assess NNK and nicotine metabolism (see Figure 1 for study schema).

Figure 1

5.2 Study Procedures:

Clinical Study visits will be scheduled at the University of Hawai'i Cancer Center clinic, however, if participants are unable to attend the clinic visit, home visits will be completed.

Visit 1 (Baseline)

At the first Clinical Study visit, the following procedures will be administered:

1. Participants will be provided detailed information about the study, and asked to sign the Study 2 Consent Form. Medical History, Concomitant Medications and Tobacco Use Exposure Update will be reviewed for any changes in health since last contact following consent procedures.
2. Timeline Follow-Back will be administered to assess the last two weeks of cigarettes and other tobacco/nicotine products, other combusted products or other drugs.
3. Provide the following supplies and instructions for the collection of the 24 hour baseline urine sample to obtain baseline sample while smoking usual brand cigarettes:

- a. Two 24h urine collection 1500 mL containers (no preservative) to collect the urine for **Sample 1** (the second container is provided in case the participant collects over 1500 mL of urine).
- b. For women: Specimen collection commode that can be placed over the toilet that will allow easy capture of urine.

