 - Smoke only the study cigarettes and to use no other nicotine-containing products or combustibles over the 7-day intervention period.
 - Smoke approximately the same number of cigarettes per day as when smoking their usual brand of cigarettes and to try to maintain this rate of smoking for the duration of the study.
 - Collect all study cigarette spent filters (butts). Return of all used cigarette butts in dated ziplock collection baggies at next clinic visit. Return all unsmoked cigarettes and empty cigarette packs. This allows for verification of amount of study cigarettes smoked.

Additional Procedures for Visit 4 and 5

1. Blood draw (2 lavender and 1 red top)

Additional Procedures for Visit 6

1. Provide tobacco cessation materials to the participant and advise to set a quit date.
2. Arrange for study compensation.

Phone follow-up – Visit 7

The participant will be called two to four days after going off of the study cigarettes to assess for any health changes or adverse events.

1. Administer Health Changes Questionnaire to assess any change in health since last visit.
2. Administer Adverse Event checklist.

Table of Study Procedures

		CLINICAL STUDY (N=20 Japanese Americans)										
		OBS ¹	BL ²	Days on Study Cigarettes								
STUDY DAY		0	1	2	3	4	5	6	7	8	11	
Clinic Visits		1	2		3		4	5	6	5	6	Phone Follow-up
Telephone screening	X											
Consent form	X	X										
Questionnaires ³	X											
Tobacco Exposure and History Interview	X	X ⁴										
Environmental Exposures	X											
48 food recall	X											
First void urine	X											
Oral cell collection	X											
Blood draw	X								X	X		
Body Mass Index (ht & wt)	X											
Medical History		X ⁴										
Concomitant Medications		X ⁴										
Carbon Monoxide	X	X	X		X		X	X	X			
Vital signs	X	X	X		X		X	X	X	X		
Adverse effects			X		X		X	X	X	X	X	
Health changes & Timeline Follow-Back		X	X		X		X	X	X	X	X	
Dispense study cigarettes				X		X		X	X			
Smoke study cigarettes ⁵		X ⁴	X	X	X	X	X	X	X	X		
Collect study cigarette butts		X	X	X	X	X	X	X	X	X		
Return study cigarette butts					X		X	X	X	X		
Start 24h urine collection		X				X	X	X				
Return 24h urine			X				X	X	X	X		
Daily smoking diary	X	X	X	X	X	X	X	X	X	X		

¹OBS= Observational Sample Collection Study Data collected during Study 1 will be used for Study 2;

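### Section 14.1 claims 80% power at about 0.9 SD, but 20 completers in two groups give about 48% power there and 80% only at about 1.32 SD

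*Combined protocol and SAP*

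**What the plan says.** Section 14.1 (Statistical considerations) plans a comparison of mean NNK α-hydroxylation between two CYP2A6 groups. It says that power depends on the "size of the group difference compared to the within-group variability" and, assuming normality, claims "80 percent power to detect a difference in group means amounting to about 0.9 standard deviations of the distribution". It gives no number per group, no significance level, no sidedness and no numerical SD. It also plans adjustment for age, sex, race, total nicotine equivalents (TNE), BMI and other confounders, without saying how much variance these are expected to explain.

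The size is given in four places, each time for the whole study:

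- Study Synopsis, accrual goal: "20 completed participants".
- Section 4.1: "Japanese American smokers (N=20 completers) will be recruited from the 100+ Japanese Americans participating in Study 1".
- Section 5.2, Table of Study Procedures: "CLINICAL STUDY (N=20 Japanese Americans".
- Section 9.1: "Up to 50 participants will be consented in order to complete 20 participants".

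Section 5.1 sets up the two groups: "One group will be smokers with very low or no CYP2A6 activity and the other will have relatively high activity". It fixes no split between them. On expected frequencies it says "28% had a ratio >3 and 15% <0.6 expected for JA smokers in the previous MEC sample", and in the same sentence also gives 12% for the low-activity group.

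**The concern.** A difference of 0.9 SD at 80% power is roughly what 20 participants per group would detect. Here 20 is the total, so each group has about half that. The 20 are completers, so the larger number to be consented does not close the gap.

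This is the plan's only power statement, and it supports the first primary endpoint in Section 3.1, the effect of CYP2A6 on NNK α-hydroxylation. A reader who relies on it would take a non-significant result as fair evidence against a difference of 0.9 SD. At the planned size, such a result would be about as likely as not when that difference is real. Section 15.2 has a monitoring board that includes a statistician begin by reviewing the protocol; it would be working from the wrong figure.

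**Working it through.** **Inputs from the document.** Stated power 80% and stated difference 0.9 SD, with the SD taken within group (Section 14.1); 20 completers in total (Synopsis, Sections 4.1, 5.2 and 9.1); two groups (Section 5.1).

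**Assumptions, because the plan is silent.** Split 10/10, two-sided alpha 0.05, equal variances, no covariate adjustment. Each is varied below except equal variances, which is taken up with the objections.

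**Method.** Two-sample t-test by the noncentral t distribution:

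- degrees of freedom: df = n1 + n2 − 2
- noncentrality: δ = d / √(1/n1 + 1/n2), where d is the difference in SD units
- power: the probability that |T| exceeds the critical value t(1 − α/2, df)

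**Step 1: trying to reproduce the stated figure.** With 20 per group, df = 38 and δ = 0.9/√(2/20) = 2.85. Power is 79.2%, and the difference detectable at 80% power is 0.909 SD. The normal approximation gives n per group = 2(1.960 + 0.842)²/0.9² = 19.4, rounded up to 20. By the t-test, 21 per group is the smallest equal size with at least 80% power (81.2%). The stated figure therefore matches about 20 per group, or about 40 in total. That 20 was entered as the group size is an inference.

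**Step 2: the planned size.** With 10 per group, df = 18, the critical value is 2.101 and δ = 0.9/√(2/10) = 2.01. Power is 47.8%. Power of 80% needs d = 1.325. The normal approximation is more generous but still far off: 52.1% power, and a detectable difference of (1.960 + 0.842)√(2/10) = 1.25 SD.

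**Step 3: other error rates and splits of 20.**

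| Split | Test | Power at 0.9 SD | Difference at 80% power |
|---|---|---|---|
| 10/10 | two-sided 5% | 48% | 1.32 SD |
| 8/12 | two-sided 5% | 46% | 1.35 SD |
| 7/13 | two-sided 5% | 44% | 1.39 SD |
| 5/15 | two-sided 5% | 38% | 1.53 SD |
| 10/10 | one-sided 5% | 61% | 1.16 SD |
| 10/10 | one-sided 10% | 75% | 0.97 SD |

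To reach 80% at 0.9 SD with 10/10, alpha would have to be about 0.13 one-sided or 0.26 two-sided. The unequal splits are illustrative, but imbalance is plausible: Section 5.1 expects 12–15% of Japanese American smokers in the low-activity group and 28% in the high-activity group.

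**Step 4: other ways the figure might have arisen.**

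- *Covariate adjustment.* Four covariates that explain no variance cost 4 df: 46.6% power and 1.348 SD. To bring the detectable difference down to 0.9 SD they would have to explain 1 − (0.9/1.325)² = 54% of the within-group variance, or 1 − (0.9/1.348)² = 55% allowing for the lost df. The plan claims no such figure.
- *Averaging the three 24-hour urines collected on study cigarettes.* Solving 1.325 × √((1 + 2ρ)/3) = 0.9 gives ρ = 0.19, so the within-person correlation could be at most about 0.19 (0.41 with a one-sided 5% test). The plan does not mention averaging.
- *SD of the pooled distribution.* If 0.9 refers to the SD of both groups combined, the within-group difference is 0.9/√(1 − 0.9²/4) = 1.008 SD and power is 57%. Section 14.1 in any case refers to within-group variability.

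**The case against.** **The trial may be adequate despite the error.** It contrasts extremes of CYP2A6 activity (ratio below 0.6 against above 3.0) and predicts a large reduction in α-hydroxylation in the low-activity group. Section 2.3 cites up to 70% inhibition by CYP2A6 antibodies in liver microsomes. The second primary outcome, the metabolic profile, is descriptive and does not rest on the power figure. This stands as far as it goes, but the plan gives neither an SD nor an expected difference in SD units, so adequacy cannot be judged either way. The descriptive label is attached to the profiling aim, not to the group comparison.

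**The prediction is directional and alpha is unstated.** A one-sided 10% test comes close, at 75% and 0.97 SD. It still falls short, and the plan does not state that it is intended.

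**The figure of 1.32 SD is not for the planned, adjusted analysis.** This is fair. Section 2.3 reports a direct relation between CYP2A6 genotype and TNE in Japanese Americans, so TNE is likely to be correlated with group. As an assumed illustration, if covariates explained 20% or 30% of group membership and none of the outcome variance, with 4 df lost, the detectable difference would be about 1.51 or 1.61 SD. Outcome variance explained by the covariates would work the other way. The restated figure should be labelled unadjusted.

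**A 10/10 split is best only under equal variances.** Also fair. If the low-activity SD were 0.7 of the other (assumed), 8/12 would give a slightly smaller variance of the difference than 10/10: 0.49/8 + 1/12 = 0.145 against 0.49/10 + 1/10 = 0.149. The effect is small and does not bring 0.9 SD within reach.

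**Conclusion.** The concern holds. The power claim in Section 14.1 cannot be obtained from 20 completers in two groups. With 10 per group, equal variances and an unadjusted two-sided 5% t-test, power at 0.9 SD is about 48% rather than 80%, and the difference detectable with 80% power is about 1.32 SD, roughly 47% larger than stated (1.325/0.9 = 1.47). The probability of missing a true 0.9 SD difference is about 52%, not 20%. The size of the gap depends on the assumed alpha, sidedness and split, but its existence does not: none of the usual choices checked recovers the claim. The error lies in the stated detectable difference; whether 20 completers suffice for the effect expected cannot be determined from the document.

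**What to change.** Replace the power sentence in Section 14.1 with one that states the number per group, alpha and sidedness together with the matching figure. For example: *With 10 completers per group and an unadjusted two-sided 5% t-test assuming equal variances, the study has 80% power to detect a difference of about 1.32 within-group SD (about 48% power at 0.9 SD).* If another error rate was intended, state it with its own figure (one-sided 5%: about 1.16 SD, with 61% power at 0.9 SD). If the sponsor relies on covariate adjustment, state the assumed variance explained and the assumed correlation of the covariates with group.

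Add one line, in Section 5.1 or 9.1, giving 10 completers per activity group as the target. It is better worded as a target than as a cap on the high-activity group: if only 7 low-activity smokers complete, 7/13 detects 1.39 SD and 7/10 detects 1.48 SD (two-sided 5%).

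The correction needs no change to procedures or to the total of 20. Its only cost is a less favourable stated detectable difference. Retaining 80% power at 0.9 SD instead would need about 21 completers per group (two-sided 5%) or 16 per group (one-sided 5%).
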